## **16.2 Laboratory Test Abnormalities**

Laboratory abnormalities that constitute an AE in their own right (considered clinically meaningful, induce clinical signs or symptoms, require concomitant therapy, or require changes in study drug) should be recorded on the Adverse Event form in the eCRF. Whenever possible, a diagnosis rather than a symptom should be provided (eg, "anemia" instead of "low hemoglobin"). Laboratory abnormalities that meet the criteria for AEs should be followed until they have returned to normal or an adequate explanation of the abnormality is found. When an abnormal laboratory test result corresponds to a sign or symptom of a previously reported AE, it is not necessary to separately record the laboratory test result as an additional event.

Laboratory abnormalities that do not meet the definition of an AE should not be reported as AEs. A Grade 3 or 4 AE does not automatically indicate an SAE unless it meets the definition of serious, as defined in Section 16.3.1. A dose modification for the laboratory abnormality may be required (see Section 12.1.3) and should not contribute to the designation of a laboratory test abnormality as an SAE.

## 16.3 Serious Adverse Events

### 16.3.1 Definitions

An SAE is defined as an event that meets at least 1 of the following criteria:

- Is fatal or life-threatening.
- Requires inpatient hospitalization or prolongation of existing hospitalization, unless hospitalization is a result of:
  - A routine treatment or monitoring of the studied indication not associated with any deterioration in condition.
  - An elective surgery or preplanned treatment for a pre-existing condition that is unrelated to the indication under study and has not worsened since signing the ICF.
  - A treatment on an emergency outpatient basis for an event not fulfilling any of the definitions of a SAE and not resulting in hospital admission.
  - Any social reasons and respite care, in the absence of any deterioration in the subject's general condition.
  - Results in persistent or significant disability, incapacity, or a substantial disruption of a person's ability to conduct normal life functions.
  - Constitutes a congenital anomaly or birth defect.
  - Is considered to be an important medical event or a medically significant event that may not result in death, be immediately life-threatening, or require hospitalization but may be considered serious when, based on appropriate medical judgment, the event may jeopardize the subject or may require medical or surgical intervention to prevent 1 of the outcomes listed above.

### 16.3.2 Reporting

For Parts 1a and 2, every SAE, regardless of suspected causality (eg, relationship to study drug(s) or study procedure or disease progression), occurring after the subject has signed the ICF through 30 days after the last dose of study treatment, or until the subject receives a new anticancer therapy (whichever occurs earlier), must be reported to the sponsor (or designee) within **24 hours** of learning of its occurrence, unless otherwise specified by the Protocol.

For Parts 1b and 3, every SAE, regardless of suspected causality (eg, relationship to study drug(s) or study procedure or disease progression), occurring after the subject has signed the ICF through 90 days after the last dose of study treatment, or within 30 days after the last dose of study treatment if the subject receives a new anticancer therapy (whichever occurs earlier), must be reported to the sponsor (or designee) within **24 hours** of learning of its occurrence, unless otherwise specified by the Protocol.

Any SAEs occurring more than 30 days [Parts 1a and 2 only] or 90 days [Parts 1b and 3 only] after the last dose of study treatment should be reported to the sponsor or its designee only if the investigator suspects a causal relationship to the study drug.

Information about all SAEs is collected and recorded on the Adverse Event form of the eCRF. The investigator must assess and record the causal relationship of each SAE to the study treatment. Relatedness will be assessed for each of INCB001158 (all Parts) and pembrolizumab (Parts 1b and 3 only).

The investigator must also complete the Incyte Serious Adverse Event Report Form, in English, and send the completed and signed form to the sponsor or designee within 24 hours of becoming aware of the SAE. The investigator must provide a causality assessment, that is, assess whether there is at least a reasonable possibility that the SAE is related to the study treatment: suspected (yes) or not suspected (no). Refer to the Incyte Reference Guide for Completing the Serious Adverse Event Report Form.

The contact information of the sponsor's study-specific representatives is listed in the investigator manual provided to each site. The original copy of the SAE Report Form and the confirmation sheet must be kept at the study site.

Investigational site personnel must report any new information regarding the SAE within 24 hours of becoming aware of the information in the same manner that the initial SAE Report Form was sent. Follow-up information is recorded on an amended or new SAE Report Form,

with an indication that it is follow-up to the previously reported SAE and the date of the original report. The follow-up report should include information that was not provided on the previous SAE Report Form, such as the outcome of the event (eg, resolved or ongoing), treatment provided, action taken with study drug because of the SAE (eg, dose reduced, interrupted, or discontinued), or subject disposition (eg, continued or withdrew from study participation). Each recurrence, complication, or progression of the original event should be reported as follow-up to that event, regardless of when it occurs.

If the SAE is not documented in the IBs for the study treatments (new occurrence) and is thought to be related to at least one of the study treatments, the sponsor or its designee may urgently require further information from the investigator for reporting to health authorities. The sponsor or its designee may need to issue an Investigator Notification (IN) to inform all investigators involved in any study with the same drug that this SAE has been reported. Suspected Unexpected Serious Adverse Reactions (SUSARs) will be collected and reported to the competent authorities and relevant ethics committees in accordance with Directive 2001/20/EC, or as per national regulatory requirements in participating countries.

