## 7.2 Exclusion Criteria

1. Any other current or previous malignancy within the past three years except a) adequately treated basal cell or squamous cell skin cancer, b) carcinoma *in situ* of the cervix, c) prostate cancer with stable prostate specific antigen (PSA) levels for 3 years, d) or other neoplasm that, in the opinion of the Principal Investigator and with the agreement of the Medical Monitor, will not interfere with study-specific endpoints.
2. Cytotoxic chemotherapy, tyrosine kinase inhibitor (or other targeted anti-cancer agent), radiation therapy, or hormonal therapy within 14 days or 5 half-lives, whichever is longer, prior to Cycle 1 Day 1 (42 days for nitrosoureas or mitomycin C).

3. Immunotherapy or biological therapy (e.g., monoclonal antibodies) within 21 days prior to Cycle 1 Day 1
  - EXCEPTION: Washout of anti-PD-1 therapy is NOT required in Part 1b Dose Escalation or the Part 3 Expansion Cohorts.
4. Treatment with an unapproved investigational therapeutic agent within 21 days (or 5 half-lives for small molecule agents) prior to Cycle 1 Day 1
  - EXCEPTION: Washout of anti-PD-1 therapy is NOT required in Part 1b Dose Escalation or the Part 3 Expansion Cohorts.
5. Has a diagnosis of immunodeficiency or any condition requiring systemic treatment with either corticosteroids ( $> 10$  mg daily prednisone equivalent) or other systemic immunosuppressive medications within 14 days prior to the first dose of study treatment. Inhaled steroids and adrenal replacement steroid doses  $\leq 10$  mg daily prednisone equivalent are permitted in the absence of active autoimmune disease.
6. Concomitant therapy with valproic acid/valproate-containing therapies.
7. Concomitant therapy with allopurinol and other xanthine oxidase inhibitors
8. Exclusion criterion deleted in Protocol Amendment 2-EU.
9. Patients with symptomatic ascites or pleural effusion requiring intermittent paracentesis or thoracentesis. A patient who is clinically stable following treatment for these conditions (including therapeutic thoraco- or para-centesis) is eligible.
10. Unable to receive medications *per os* (PO)
11. Unstable/inadequate cardiac function:
  - Myocardial infarction or symptomatic ischemia within the last 6 months
  - Uncontrolled or clinically significant conduction abnormalities (e.g., ventricular tachycardia on antiarrhythmics are excluded; 1st degree AV block or asymptomatic LAFB/RBBB are eligible)

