***Disease-specific Exclusion Criteria:***

***Part 1b AND Part 3***

1. Intolerance to prior anti-PD-1/PD-L1 therapy including 1) discontinuation due to immune-related toxicity or, 2) immune-related toxicities that required intensive or prolonged immunosuppression (including, high-dose IV corticosteroids, > 2 mo of immunosuppressive corticosteroids (i.e., equivalent of >10mg oral prednisone daily) or the addition of potent immunosuppression to corticosteroids (e.g., mycophenolate mofetil/CellCept or infliximab) to manage.
2. Prior severe hypersensitivity ( $\geq$  Grade 3) to pembrolizumab and/or any of its excipients or prior severe hypersensitivity reaction to any other monoclonal antibody (mAb).
3. Has a history of (non-infectious) pneumonitis that required steroids or current pneumonitis.
4. Has a history of interstitial lung disease.
5. Has received transfusion of blood products (including platelets or red blood cells) or administration of colony stimulating factors (including G-CSF, GM-CSF or recombinant erythropoietin) within 2 weeks prior to study Day 1.

6. Active autoimmune disease that has required systemic treatment in past 2 years (i.e. with use of disease modifying agents, corticosteroids or immunosuppressive drugs). Replacement therapy (eg, thyroxine, insulin, or physiologic corticosteroid replacement therapy for adrenal or pituitary insufficiency, etc.) is not considered a form of systemic treatment.

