#### **11.5 Follow-Up**

##### **11.5.1 Safety Follow-Up**

The safety follow-up period is the interval between the EOT visit and the scheduled follow-up visits, which should occur 30 to 37 days (all patients) and 90 to 97 days (Parts 1b and 3 only) after the final dose of study treatments.

Adverse events (all patients) and SAEs (Parts 1a and 2 only) must be reported up until the date of the 30-day follow-up visit, or until toxicities resolve, return to baseline, or are deemed irreversible, whichever is longer.

Serious adverse events (Parts 1b and 3 only) must be reported up until the date of the 90-day follow-up visit, or until toxicities resolve, return to baseline, or are deemed irreversible, whichever is longer.

Reasonable efforts should be made to have the patient return for the follow-up visits and report any AEs that may occur during this period. If the patient cannot return to the site for the safety follow-up visit (eg, lives far away), the patient should be contacted by telephone for assessment of AEs and SAEs. Sites should document this contact in the source.

If a patient is scheduled to begin a new anticancer therapy before the end of the 90-day safety follow-up period, the safety follow-up visit should be performed before new anticancer therapy is started. Once new anticancer therapy has been initiated, the patient will have completed the follow-up period.

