### **15.3 Analysis Populations**

#### **15.3.1 Safety Population**

All patients who receive at least 1 dose of INCB001158 or pembrolizumab will be included in the analysis of safety, regardless of the duration of treatment.

AE and laboratory data from all patients in the safety population will be evaluated for safety. Patients from dose escalation will be combined with patients receiving the same dose and schedule from cohort expansion for safety evaluation. Patients with moderate renal impairment in Part 1c will be evaluated separately. Data will be tabulated to examine the frequency, organ systems affected, and relationship to study treatments. No formal interim analysis is planned; however, safety data will be examined on an ongoing basis to ensure safety of the study patients and compliance with the trial dose escalation and expansion rules.

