The occurrence of AEs should be sought by nondirective questioning of the subject during the screening process after signing the ICF and at each visit during the study. Adverse events may also be detected when they are volunteered by the subject during the screening process or between visits, or through physical examination, laboratory test, or other assessments. To the extent possible, each AE should be evaluated to determine:

- The severity grade (CTCAE Grade 1 to 5).
- Whether there is at least a reasonable possibility that the AE is related to the study treatment: suspected (yes) or not suspected (no). Relatedness will be assessed for each of INCB001158 (all Parts) and pembrolizumab (Parts 1b and 3 only).
- The start and end dates, unless unresolved at final follow-up.
- The action taken with regard to study drug.
- The event outcome (eg, not recovered/not resolved, recovered/resolved, recovering/resolving, recovered/resolved with sequelae, fatal, unknown).
- The seriousness, as per serious adverse event (SAE) definition provided in Section 16.3.1.

Unlike routine safety assessments, SAEs are monitored continuously and have special reporting requirements (see Section 16.3.2).

All AEs should be treated appropriately. If an AE is treated with a concomitant medication or nondrug therapy, this action should be recorded on the Adverse Event form in the eCRF and the

treatment should be specified on the Prior and Concomitant Medications or Procedures form in the eCRF.

Once an AE is detected, it should be followed until it has resolved or until it is judged to be permanent; assessment should be made at each visit (or more frequently if necessary) of any changes in severity, the suspected relationship to the study drug, the interventions required to treat the event, and the outcome.

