**ATTACHMENT 1B: SCHEDULE OF STUDY ASSESSMENTS FOR PARTS 1B, 1C, AND 3 (INCB001158 + PEMBROLIZUMAB)**

Cycle Length = 21 Days

Visit	Screening	Cycle 1			Cycle 2	Cycle 3	Cycle 4+	End of Treatment	Follow-Up	
		Day 1	Day 8 (± 2 days) 	Day 15 (± 2 days) 					Day 1 (± 5 days) 	Day 1 (± 5 days) 
Written Informed Consent	X									
Inclusion/Exclusion Criteria	X									
Demographics and Medical History	X									
Physical Examination 	X	X	X	X	X	X	X 	X	X	X
Height	X									
Weight	X	X	X	X	X	X	X 	X	X	X
Vital Signs 	X	X	X	X	X	X	X	X	X	X
ECOG Performance Status	X	X			X	X	X 	X	X	X
Duplicate 12-lead ECG with QTcF 	X	X 		X 				X		
Urinalysis	X	X 			X	X	X	X		
Serum Chemistry levels 	X	X 	X	X	X	X	X	X		
Hematology 	X	X 	X	X	X	X	X	X		
Pregnancy Test 	X				X			X		

Visit	Screening	Cycles						End of Treatment	Follow-Up		
		Cycle 1	Cycle 2	Cycle 3	Cycle 4+	Safety	Disease Status				
	Day-21 to -1	C1D1	C1D8 (± 2 days) 	Day 15 (± 2 days) 	Day 1 (± 5 days) 	Day 1 (± 5 days) 	Day 1 (± 5 days) 	Within 28 days post treatment discontinuation	30-37 days after last dose of INCB001158 + pembrolizumab	90-97 days after last dose of INCB001158 + pembrolizumab	Q9W after discontinuation
Plasma Ammonia Levels 		X	X	X	X	X	X				
Urine Sample for Orotic Acid 		X	X	X	X	X	X				
Coagulation tests	X	X 	X	X	X	X	X	X			
Pharmacokinetic (PK) Assay 		X		X	X	X	X				
Amino Acid Panel 		X		X	X	X	X				
Pembrolizumab Dosing 		X			X	X	X				
INCB001158 Dosing 		X	X	X	X	X	X				
Radiographic Evaluation of Tumor Burden (diagnostic CT or MRI) 	X 						X 	X			X
Adverse Events		X	X	X	X	X	X	X	X	X	
Concomitant Medications	X	X	X	X	X	X	X	X	X	X	
Post-treatment anticancer therapy status									X	X	X

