  13. Patients enrolled in Parts 1b, 1c, and 3: Pembrolizumab dosing will take place on D1 of every cycle. Study treatment with pembrolizumab should be administered on Day 1 of each cycle after all procedures/assessments have been completed. All study treatments will be administered on an outpatient basis. Infusion of pembrolizumab precede INCB001158 dosing and PK analysis on C1D1 and day one of every cycle.
  14. INCB001158 is given daily, BID. During PK days, the morning dose of INCB001158 will be administered during the clinic visit after all pre-dosing procedures, including pembrolizumab administration and pre-dose PK blood sampling, has occurred. INCB001158 will be taken within 5 minutes after pembrolizumab infusion.
  15. Whenever possible, imaging should be done at the same institution/facility and with the same modality that will be used to measure response during the patient's participation in the study. The redacted copies of the reports will be submitted and the scans must be sent to a reader for exploratory analyses. If available, 1-3 redacted scan reports for scans that occurred prior to screening will be requested.
  16. Tumor assessments within 28 days prior to C1D1 will be accepted.
  17. Completed approximately every 9 weeks per RECIST v1.1 OR Modified RECIST for pleural mesothelioma. Evaluations may occur more frequently as clinically indicated.
- [REDACTED]
20. Orotic acid and plasma ammonia samples will also be collected on day one of every cycle after Cycle 4.

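### Part 1c receives pembrolizumab, but the protocol gives it no SAE reporting window, omits it from pembrolizumab attribution, and contradicts itself on its 90-day safety visit

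*Protocol*

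**What the plan says.** **Part 1c is a combination cohort.** The footnotes to Attachment 1B state "Patients enrolled in Parts 1b, 1c, and 3: Pembrolizumab dosing will take place on D1 of every cycle". Section 3.0 lists safety and tolerability of the combination as the primary objective for Parts 1b, 1c and 3. Section 15.3.1 adds "Patients with moderate renal impairment in Part 1c will be evaluated separately".

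**SAE reporting (Section 16.3.2).** One paragraph sets a 30-day all-causality window for Parts 1a and 2. The next sets a 90-day window for Parts 1b and 3, cut to 30 days if a new anticancer therapy starts. The rule for later events reads "Any SAEs occurring more than 30 days [Parts 1a and 2 only] or 90 days [Parts 1b and 3 only".

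**Causality (Sections 16.1.2 and 16.3.2).** Both sections carry the same sentence: "Relatedness will be assessed for each of INCB001158 (all Parts) and pembrolizumab (Parts 1b and 3 only".

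**90-day follow-up.** The synopsis restricts the 90-day visit to Parts 1b and 3, and so does Section 11.5.1: "90 to 97 days (Parts 1b and 3 only". Attachment 1B, whose title covers Parts 1b, 1c and 3, has a safety column headed "90-97 days after last dose of INCB001158 + pembrolizumab" with adverse events marked in it.

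**Eligibility wording (Section 7.2).** The combination exclusions are headed "Part 1b AND Part 3", and the exception to exclusions 3 and 4 says "Washout of anti-PD-1 therapy is NOT required in Part 1b Dose Escalation or the Part 3 Expansion Cohorts". Sections 5.1 and 7.1 require Part 1c patients to satisfy the criteria of one of Cohorts 3a to 3h.

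**The concern.** Safety is what Part 1c is primarily meant to measure. Its patients take two investigational treatments, yet the text that governs SAE reporting and attribution does not name the cohort. A site reading Section 16 literally cannot tell when mandatory all-causality SAE reporting ends for a Part 1c patient. It would also conclude that it need not rate events against pembrolizumab. A site reading Section 11.5.1 would not schedule a visit that Attachment 1B requires.

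Two other passages add weight. Section 12.1.3.1 warns that immune-related events can appear months after the last pembrolizumab dose, so the length of the window matters. Under Section 17.0, once the database is locked for analysis, sites report only SAEs and pregnancies for remaining patients, following Section 16.0. For those patients Section 16 is then the only operative text.

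**Working it through.** The plan states no figure to reproduce here. The check is to set each rule that depends on study part beside Part 1c.

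| Rule | Where | Parts named | Part 1c |
|---|---|---|---|
| Pembrolizumab given on Day 1 of each cycle | Attachment 1B footnotes | 1b, 1c, 3 | included |
| Combination safety as primary objective | Section 3.0 | 1b, 1c, 3 | included |
| 30-day all-causality SAE window | 16.3.2 | 1a, 2 | not named |
| 90-day all-causality SAE window | 16.3.2 | 1b, 3 | not named |
| Late-SAE rule, both brackets | 16.3.2 | 1a, 2 / 1b, 3 | not named |
| SAE reporting to the 30-day or 90-day visit | 11.5.1 | 1a, 2 / 1b, 3 | not named |
| 90-day safety visit, narrative | Synopsis, 11.5.1 | 1b, 3 | not named |
| 90–97 day safety visit, schedule | Attachment 1B | 1b, 1c, 3 | included |
| Relatedness to INCB001158 | 16.1.2, 16.3.2 | all | included |
| Relatedness to pembrolizumab | 16.1.2, 16.3.2 | 1b, 3 | not named |
| AE collection to 30 days | 11.5.1, 16.1.2 | all | included |

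Three results follow.

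1. **SAE window: undefined.** Neither window covers Part 1c. The two candidates differ by 90 − 30 = 60 days per patient. Attachment 1B does not settle the matter, because it schedules a visit but sets no mandatory reporting period.
2. **90-day visit: contradictory.** The narrative limits the visit to two parts, while the schedule includes Part 1c.
3. **Pembrolizumab attribution: excluded as written.** The restriction appears for AEs and again for SAEs, and no passage restores the separate rating for Part 1c.

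AE collection is not missing. Section 11.5.1 collects AEs in all patients to the 30-day visit or resolution. Section 16.1.2 monitors for 30 days, or until new anticancer therapy, without limit by part. (Section 11.7 says 28 days; that small discrepancy applies to every part alike.)

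For scale, the cohort has 6 evaluable patients, so one patient is 1/6 = 16.7% of it.

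**The case against.** The strongest reply is that the two-part phrase is leftover shorthand for the combination arms. Sections 11.2.1 and 13.1 use it even for pembrolizumab dosing, where nobody would conclude that Part 1c goes undosed. The summary of the amendment that added Part 1c does not list Sections 11.5.1, 16.1.2 or 16.3.2 among the updated sections, which fits an oversight. That probably explains the wording, but it does not cure it: the word *only* excludes, and sites follow the text.

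Section 16.3.2 also has duties not limited by part. All SAEs are recorded, the form goes in within 24 hours of awareness, and causality to study treatment must be assessed. Section 13.0 defines both agents as study treatments. This stands. SAE reporting is not absent for Part 1c; what is missing is the end of the all-causality window and the separate pembrolizumab rating.

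Four stronger readings are tempting, and the documents do not support them.

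- *A reader might infer that Part 1c safety data are incomplete.* AEs are collected to 30 days in every patient, and Attachment 1B adds collection at 90–97 days.
- *A reader might infer that SAP counts of pembrolizumab-related events cannot be filled.* SAP Section 8.2.1 treats an event with unspecified relationship as treatment-related. Appendix A lists its pembrolizumab-related table (3.2.10.2.2) for Parts 1b and 3 only, and SAP Section 5.1 says only that Part 1c safety data may be presented as a group.
- *A reader might infer that 60 of 90 reporting days are lost.* That assumes sites would apply the 30-day rule, which names only Parts 1a and 2.
- *A reader might infer that the combination exclusions do not apply to Part 1c.* Its patients must meet Part 3 cohort criteria, which naturally brings in the Part 3 exclusions by reference.

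Nor does renal impairment strengthen the pembrolizumab argument. The clearance concern is with INCB001158, whose relatedness is assessed in all parts. Section 10.2.2.1 reports no clinically important effect of moderate impairment on pembrolizumab clearance.

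**Conclusion.** The point holds as an internal inconsistency in the protocol's safety-reporting text. For a pembrolizumab-treated cohort whose primary objective is safety, the protocol leaves the all-causality SAE window unassigned, excludes the pembrolizumab relatedness rating, and gives conflicting instructions on the 90-day visit.

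It reaches every Part 1c patient: 6 evaluable plus replacements. No number of lost events or lost follow-up days can be derived, because the documents do not say which window sites would use. The conclusion rests on reading the part labels literally. If every site silently treats Part 1c as part of the combination arms, nothing is lost in practice, but the protocol does not tell them to. It should be corrected, because it touches a primary endpoint and the cost is small.

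**What to change.** Reconcile the synopsis and Sections 11.5.1, 16.1.2 and 16.3.2 with Attachment 1B by naming Part 1c explicitly in three places:

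- the SAE reporting window, including the late-SAE rule;
- the 90-day safety follow-up text;
- the statement on pembrolizumab relatedness, for both AEs and SAEs.

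As a clarification only, reconcile the heading of the combination exclusions and the washout exception in Section 7.2 with the Part 1c eligibility cross-reference in Sections 5.1 and 7.1. The sponsor should state which eligibility rule applies; this review proposes none.

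The cost is protocol wording. No visits are added beyond those Attachment 1B already schedules.
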